13.6.3. Efficacy

Efficacy	
Snapshot	

 • The Snapshot algorithm is intended to be primarily a virologic assessment of the endpoint, and as such follows a "virology first" hierarchy. • 'HIV-1 RNA < 50 c/mL' or 'HIV-1 RNA ≥ 50 c/mL' within an analysis window (see Table 2 and Table 3) is typically determined by the last available HIV-1 RNA measurement in that window while the participant is On-treatment in the Intervention Phase (as assigned based on Section 13.3). • When no HIV-1 RNA data is available within a window, a participant cannot be assigned to the category of 'HIV-1 RNA < 50 c/mL'. Depending on the reason for lack of data, the participant will be classified as 'HIV-1 RNA ≥ 50 c/mL' or reported as 'No Virologic Data at Week X'; in the latter case, the algorithm further classifies the nature of the missing data. Typically, a participant withdrawn (i) due to AE or, (ii) for another reason yet was suppressed at the time, will be counted as 'No Virologic Data at Week X'. Should a participant withdraw for reasons other than AE and was not suppressed at the time, they will be categorized as 'HIV-1 RNA ≥ 50 c/mL'. 	

Efficacy

 Full details of the algorithm, including the handling of special cases, are included in Appendix 9: Snapshot Algorithm Details.
Plasma HIV-1 RNA

 For summaries and analyses which use HIV-1 RNA level as a continuous measure, the logarithm to base 10 of the value will be used. HIV-1 RNA results may be provided as censored values, such as <40 or >9,999,999 c/mL. For the purposes of summary statistics, such values will be replaced by the next value beyond the limit of detection, e.g., 39 or 10,000,000 c/mL, respectively, for the given examples. Data listings will show the censored values as provided.
Confirmed Virologic Failure (CVF)

 For the purposes of clinical management in this study, CVF is defined as: 
 Rebound as indicated by two consecutive plasma HIV-1 RNA levels \geq 200 c/mL. The CVF definition is provided in the protocol Section 7.1.3 Only plasma HIV-1 RNA values determined by the central laboratory will be used to assess virologic failure.
CDC Classification for HIV-1 Infection (2014)

 CDC HIV-1 Classification at Baseline is collected in eCRF and no derivation will be performed programmatically for analysis purposes. Please refer to study protocol for detail description of CDC HIV-1 Classification.
13.6.4. Safety
Adverse Events
DAIDS Grading

 Clinical adverse events will be graded based on the Division of AIDS Table for Grading the Severity of Adult and Pediatric Adverse Events Version 2.1, March 2017, as specified in the protocol Appendix 10.2. If a grade value is expected per DAIDS but is missing in the eCRF, then the missing grade will be given an ordinal grade value of -1 for determining the maximum grade within and across preferred terms. For example: 
 if a participant has two separate instances of the same preferred term, one with grade 2 and one with missing grade, then the maximum grade for the preferred term will be set to grade 2. if a participant reports two different AE preferred terms overall, one with grade 1 and one with missing grade (where a DAIDS grade is expected), then the maximum grade across preferred terms (i.e. in the ANY EVENT row) will be set to grade 1. If a participant reports only one AE overall and this has a missing grade (where a DAIDS grade is expected), then this will be presented under a grade = missing category
Days since First Dose (Days)

 AE Start Date – Intervention Phase Treatment Start Date + 1

Adverse Events
Days since Last Dose (Days)

 AE Start Date – Date of Last Dose of Study Treatment (CAB+RPV, SOC bridging, CAB/RPV IM Injection) prior to/on the Start Date of AE + 1
Days since Phase Start

 For AEs in Intervention/Extension Phase: 
 AE Start Date - Intervention Treatment Start Date + 1 For AEs in Long-term Follow-up Phase: 
 AE Start Date – Date of Last Dose of Study Treatment Date of Last Dose of Study Treatment = max (Last IM Injection Date, Last Oral Bridging End Date [CAB+RPV, SOC ART]), only applicable to participants who permanently discontinued study treatment.
Duration (Days)

 AE Resolution Date – AE Start Date + 1
Drug-related

 If relationship is marked 'YES' on Inform/eCRF Injection site reactions will be considered as drug-related if the relationship to study drug value is missing in the eCRF.

Laboratory Parameters												

 If a laboratory value which is expected to have a numeric value for summary purposes, has a non-detectable level reported in the database, where the numeric value is missing, but typically a character value starting with '<x' or '>x' (or indicated as less than x or greater than x in the comment field) is present, the number of significant digits in the observed values will be used to determine how much to add or subtract in order to impute the corresponding numeric value. If a character value starting with "<=x", then the numeric value will be x. 
 Example 1: 2 Significant Digits = '< x' becomes x – 0.01 Example 2: 1 Significant Digit = '> x' or '>=x' becomes x + 0.1 Example 3: 0 Significant Digits = '< x' becomes x – 1 												
Lab Toxicities – DAIDS Grading												

 Toxicities will be based on the Division of AIDS (DAIDS) grading system, Version 2.1, March 2.17, as specified in the protocol of Appendix 10.2 Toxicity grades provided by the central laboratory do not distinguish between abnormally high or low criteria, when both are relevant for a particular parameter. When summarizing toxicity grades for such parameters, they will be categorized as to whether they are above or below the midpoint of normal range. 												

  
 Parameter	Below Midpoint for those \geqGrade 1	Above Midpoint for those \geqGrade 1	
   
 Glucose	Hypoglycaemia	Hypoglycaemia	
 
 Sodium	Hyponatremia	Hyponatremia	
 
 Potassium	Hypokalaemia	Hypokalaemia	
  
	Parameter	Below Midpoint for those \geq Grade 1	Above Midpoint for those \geq Grade 1	Glucose	Hypoglycaemia	Hypoglycaemia	Sodium	Hyponatremia	Hyponatremia	Potassium	Hypokalaemia	Hypokalaemia
Parameter	Below Midpoint for those \geq Grade 1	Above Midpoint for those \geq Grade 1										
Glucose	Hypoglycaemia	Hypoglycaemia										
Sodium	Hyponatremia	Hyponatremia										
Potassium	Hypokalaemia	Hypokalaemia										

Other Safety Endpoints	
Corrected QT (QTc)	

 When not entered directly in the eCRF, corrected QT intervals by Bazett's (QTcB) and Fridericia's (QTcF) formulas will be calculated, in msec, depending on the availability of other measurements. If RR interval (in msec) is provided, then missing QTcB and/or QTcF will be derived as 	
$QTcB = \frac{QT}{\sqrt{RR/1000}}$ $QTcF = \frac{QT}{\sqrt[3]{RR/1000}}$	

 where uncorrected QT interval is also measured in msec. If RR interval is not provided directly and one of QTcB or QTcF has been entered, then RR interval can be obtained from the above formulas and used to calculate the other correction method value; i.e., 	
$QTcB = \sqrt{\frac{QTcF^3}{QT}}$ $QTcF = \sqrt[3]{QT \cdot QTcB^2}$	
Extent of Exposure	

 Exposure to CAB+RPV (oral lead-in or oral bridging) and CAB LA+RPV LA will be calculated from the IP eCRF pages. 	
For Intervention Phase: 
 Exposure to CAB+RPV Oral Lead-in = IP (oral lead-in) stop date - IP (oral lead-in) start date +1 Exposure to CAB LA + RPV LA = Number of IP injection visits received during the Intervention Phase (up to but not including injections administered at Month 13) Exposure to SOC oral bridging: Duration of the SOC ART medication taken as oral bridging during the Intervention Phase. If the SOC oral bridging is taken in different periods during the Intervention Phase, the duration will be calculated by the sum of non-overlapped periods. Exposure to CAB+RPV Oral Bridging (COVID-19 Related): Duration of the CAB+RPV taken as oral bridging for reasons related to COVID-19 during the Intervention Phase. If COVID-19 related CAB+RPV oral bridging is taken in different periods during the Intervention Phase, the duration will be calculated by the sum of the non-overlapped periods. Exposure to CAB+RPV Oral Bridging (Non COVID-19 Related): Duration of the CAB+RPV taken as oral bridging for reasons not related to COVID-19 during the Intervention Phase. If non COVID-19 related CAB+RPV oral bridging is taken in different periods during the Intervention Phase, the duration will be calculated by the sum of the non-overlapped periods. Overall Exposure to Study Treatment: min [Date of Latest Intervention Phase Visit up to and including Month 13, max (Date of Last Injection + 35, Date of Last Dose of Oral CAB+RPV, Date of Last Dose of SOC Oral Bridging)] – min (Start Date for Oral lead-in CAB+RPV, Date of First CAB/RPV Injection) + 1 
 Note: Conditions in the above formula pertaining to Last Injection/Last Dose of Oral CAB+RPV/Last Dose of SOC Oral Bridging are only applicable to those who permanently discontinued study treatment. 	

Other Safety Endpoints	

 • Overall Exposure to CAB + RPV = Overall Exposure to Study Treatment – Exposure to SOC Oral Bridging 	
For Intervention + Extension Phase:	

 • Exposure to CAB LA + RPV LA = Number of IP injection visits received during Intervention Phase and Extension Phase • Exposure to SOC or CAB+RPV Oral Bridging during the Intervention and Extension Phase will be calculated similarly to that during the Intervention Phase except that the exposure includes both Intervention and Extension Phase. • Overall Exposure to Study Treatment: min [Date of Latest Intervention/Extension Phase Visit, max (Date of Last Injection + 35, Date of Last Dose of Oral CAB+RPV, Date of Last Dose of SOC Oral Bridging)] – min (Start Date for Oral lead-in CAB+RPV, Date of First Study Injection) + 1 
 ○ Note: Conditions in the above formula pertaining to Last Injection/Last Dose of Oral CAB+RPV/Last Dose of SOC Oral Bridging are only applicable to those who permanently discontinued study treatment. • Overall Exposure to IP = Overall Exposure to Study Treatment – Exposure to SOC Oral Bridging • Duration of dosing in participant years will be calculated as the sum of participant duration of dosing in days (across all participants)/365.25 	

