8.1. Adverse Events Analyses

Adverse events analyses including the analysis of adverse events (AEs), Serious (SAEs), COVID-19 AEs, and other significant AEs will be based on GSK Core Data Standards. The details of the planned displays are provided in Appendix 13: List of Data Displays.

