13.7.2. Handling of Missing Data

Element	Reporting Detail
General	
 Missing data occurs when any requested data is not provided, leading to blank fields on the collection instrument: 
 These data will be indicated by the use of a “blank” in participant listing displays. Unless all data for a specific visit are missing in which case the data is excluded from the table. Answers such as “Not applicable” and “Not evaluable” are not considered to be missing data and should be displayed as such.
Outliers	
 Any participants excluded from the summaries and/or statistical analyses will be documented along with the reason for exclusion in the clinical study report.

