3.13.	Safety	AE3	Summary Drug-Related Adverse Events by Overall Frequency	ICH E3	M12, EOS
3.14.	Safety	AE5B	Summary of Drug-Related Adverse Events by System Organ Class and Maximum Grade	ICH E3	HL, M12, EOS
3.15.	Safety	AE5B	Summary of Drug-Related Adverse Events by System Organ Class and Maximum Grade — Excluding Study Drug Injection Site Reactions		M12, EOS
3.16.	Safety	AE15	Summary of Common (>=5%) Non-serious Adverse Events by System Organ Class and Preferred Term (Number of Subjects and Occurrences)	FDAAA, EudraCT	M12, EOS
3.17.	Safety	AE3	Summary of Common (>=1%) Drug-Related Grade 2-5 Adverse Events by Overall Frequency	ICH E3	M12, EOS
3.18.	Safety	AE3	Summary of Non-Serious Drug-Related Adverse Events by Overall Frequency	Plain Language Summary requirements.	M12, EOS

Safety: Tables					
No.	Population	GSK Standard/ Example Shell	Title	Programming Notes	Deliverable
Serious and Other Significant Adverse Events					
3.19.	Safety	AE5B	Summary of Serious Adverse Events by System Organ Class and Maximum Grade	ICH E3	HL, M12, EOS
3.20.	Safety	AE16	Summary of Serious Adverse Events by System Organ Class and Preferred Term (Number of Subjects and Occurrences)	FDAAA, EudraCT	M12, EOS
3.21.	Safety	AE1	Summary of Adverse Events Leading to Permanent Discontinuation of Study Treatment or Withdrawal from Study by System Organ Class and Preferred Term	GSK Statistical Display Standard	HL, M12, EOS
3.22.	Safety	AE20	Summary of Serious Fatal and Non-Fatal Drug-Related Adverse Events by Overall Frequency	Plain Language Summary requirements.	M12, EOS
Injection Site Reaction Adverse Events					
3.23.	Safety	201584/primary_7/T3.40	Summary of Study Drug Injection Site Reaction Adverse Events (Event-level Summary)		HL, M12, EOS
3.24.	Safety	201584/primary_7/T3.43	Summary of Subject-level Characteristics of Study Drug Injection Site Reaction Adverse Events – Overall and Common		HL, M12, EOS
3.25.	Safety	201584/primary_7/T3.46	Summary of Study Drug Injection Site Reaction Adverse Events by Visit and Maximum Severity – Overall and Common		HL, M12, EOS

Safety: Tables					
No.	Population	GSK Standard/ Example Shell	Title	Programming Notes	Deliverable
Laboratory: Chemistry					
3.26.	Safety	LB1	Summary of Chemistry Values	Includes pre-specified parameters repeated in conventional units. Includes baseline values	M12, EOS
3.27.	Safety	LB1	Summary of Chemistry Changes from Baseline	ICH E3	M12, EOS

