18.	Safety	PSRAE4	Listing of Possible Suicidality-Related Adverse Event Data (Section 4)	Add Phase	M12
19.	Safety	PSRAE5	Listing of Possible Suicidality-Related Adverse Event Data (Section 5-Section 8)	Add Phase	M12
20.	Safety	201584/primary_07/L22	Listing of Changes in Intensity/Grades of Study Drug Injection Site Adverse Events	Remove phase treatment	M12, EOS
21.	Safety	AE8	Listing of COVID-19 Adverse Events	Add Phase/Period, Side/Drug, see gsk1265744/mid207966/primary_15/L19	HL, M12, EOS
22.	Safety	PAN12	Listing of COVID-19 Assessments and Symptom Assessments		M12, EOS
23.	Safety	PAN5	Country Level Listing of Start Dates of COVID-19 Pandemic Measures	For EOS: change the title to be "Country Level Listing of Dates of Waves of COVID-19 Pandemic Measures" and use the PAN5A shell.	M12, EOS
Serious and Other Significant Adverse Events					
24.	Safety	AE8	Listing of Fatal Serious Adverse Events	ICH E3 Add Phase/Period, Side/Drug	M12, EOS

ICH: Listings					
No.	Population	GSK Standard / Example Shell	Title	Programming Notes	Deliverable
25.	Safety	AE8	Listing of Non-Fatal Serious Adverse Events	ICH E3 Add Phase/Period, Side/Drug	M12, EOS
26.	Safety	AE14	Listing of Reasons for Considering as a Serious Adverse Event	ICH E3	M12, EOS
27.	Safety	AE8	Listing of Adverse Events Leading to Withdrawal from Study / Permanent Discontinuation of Study Treatment	ICH E3 Add Phase/Period, Side/Drug	M12, EOS
28.	Safety	AE8	Listing of All Adverse Events with Completely Missing Onset Date, Missing Relationship to Study Treatment, Severity and/or Grade	ICH E3 Add Phase/Period, Side/Drug, see gsk1265744/mid207966/primary_15/L19	M12
Laboratory					
29.	Safety	UR2	Listing of Urinalysis Data for Subjects with Any Value of Potential Clinical Importance	ICH E3 Include Grade Note: Potential Clinical Importance is defined as: 1. Increase in Protein (dipstick) or Occult Blood (dipstick) post-baseline relative to baseline 2. Increase in any DAIDS graded values for Protein, Occult Blood or Glucose relative to baseline 3. If microscopy is performed.	M12, EOS

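### Only injection site reactions have a missing-causality rule, so any other adverse event with a blank relationship is left out of the drug-related tables, whose counts can then be too low

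*SAP*

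**What the plan says.** The drug-related entry in SAP Section 13.6.4 (Safety, Adverse Events) has two lines. An AE qualifies "If relationship is marked 'YES' on Inform/eCRF". The second line deals with a blank field for one event type: "Injection site reactions will be considered as drug-related if the relationship to study drug value is missing in the eCRF".

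No other section supplies a value for missing causality. Section 13.7.2 says of missing fields in general that "These data will be indicated by the use of a “blank” in participant listing displays", and Section 13.7.2.1 imputes partial AE dates only. Section 8.1 refers the AE analyses to company standards that are not part of the document: "Serious (SAEs), COVID-19 AEs, and other significant AEs will be based on GSK Core Data Standards".

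The plan does foresee blank causality. Listing 28 in Section 13.13.11 is titled "Listing of All Adverse Events with Completely Missing Onset Date, Missing Relationship to Study Treatment, Severity and/or Grade". In the amended plan its deliverable is the Month 12 analysis (M12) only.

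Six tables in Section 13.13.7 depend on the definition: 3.13, 3.14, 3.15, 3.17, 3.18 and 3.22. All six are due at M12 and end of study (EOS), and Table 3.14 is also a Month 12 headline display.

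**The concern.** A definition that requires a YES, with one named exception, has a definite effect on blank records: an injection site reaction (ISR) goes in and anything else stays out. The cautious default therefore applies to expected local reactions and not to systemic or serious events. Leaving out events of unknown causality can only reduce a drug-related count, and with a single treatment group no comparator carries the same omission.

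The tables at stake include "Summary of Serious Fatal and Non-Fatal Drug-Related Adverse Events by Overall Frequency" (Table 3.22). That table and Table 3.18 are marked for plain language summary use, where a reader is unlikely to consult a listing.

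The same section shows that missing AE attributes can be handled generally. A missing grade has a rule for every AE that should carry one, ending in a separate missing category.

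**Working it through.** The SAP states no expected drug-related rate and no number of blanks, so there is no figure to reproduce. The check has two parts.

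**1. The rule applied to each case (Section 13.6.4)**

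| Event | Relationship field | Result under the text |
|---|---|---|
| Any AE | YES | In the drug-related tables |
| ISR | Blank | In, by the explicit rule (not shown in Table 3.15, which excludes ISRs) |
| Any other AE | Blank | Does not meet the definition, so out of all six tables |

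**2. Possible size**

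Inputs:
- N = 115, single treatment group (SAP Sections 2.3 and 5.1).
- x = participants with an AE marked YES (illustrative).
- m = participants whose only candidate AE has a blank relationship. This is not given; 0 to 5 is assumed.

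The literal rule reports x/115. Counting blanks as related gives (x + m)/115, so the difference is m/115:
- m = 0: no difference.
- m = 1: 1/115 = 0.87 points.
- m = 5: 5/115 = 4.3 points.

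Illustrations with Clopper-Pearson 95% limits:

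| x | m | Literal rule, x/115 | Blanks as related, (x + m)/115 |
|---|---|---|---|
| 2 | 1 | 1.74% (0.21 to 6.14) | 2.61% (0.54 to 7.43) |
| 10 | 5 | 8.70% (4.25 to 15.41) | 13.04% (7.49 to 20.60) |

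The relative effect is largest for rare terms. With one YES and one blank, the table shows 1 of 2 participants, half the count. With two YES and one blank it shows 2 of 3, a cut of one third.

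**Threshold in Table 3.17.** The table is "Summary of Common (>=1%) Drug-Related Grade 2-5 Adverse Events by Overall Frequency". One participant is 1/115 = 0.87%, below the cut; two are 2/115 = 1.74%, above it. A Grade 2-5 term with one YES and one blank would appear if blanks counted as related, and does not appear under the literal rule.

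**The case against.** Several points on the other side are sound.

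- **There may be no blanks.** Section 3.2 requires data cleaning and database freeze before both the Month 12 and EOS analyses. Planning Listing 28 does not show that such records exist. This stands, and is why the range starts at zero.
- **Company standards may cover the case.** Section 8.1 relies on standards that cannot be seen here, so the gap cannot firmly be called an error. If they already counted blanks as related, however, the ISR sentence would be redundant. Its presence suggests a different default, or at best an unstated one.
- **The difference between event types has a rationale.** Section 8.1.1 limits ISRs of interest to those from study drug injections, so the event type itself points to the drug. A blank on a COVID-19 event or an injury does not. This explains a default for ISRs but not the lack of any rule for other events. It also means that counting all blanks as related could include some unrelated events.
- **No event disappears from the report.** All AEs are in Tables 3.7 and 3.8 and Listing 13, serious AEs in 3.19 and 3.20, and AEs leading to discontinuation in 3.21. Depression and rash have Tables 3.44 and 3.50, and liver laboratory abnormalities Table 3.35. This stands and limits the severity.
- **Listing 28 shows the affected records.** It does so at Month 12 only, and it changes no table count.

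A reader might also infer that Tables 3.14 and 3.15 treat the same blank field in opposite ways. They do not. A blank non-ISR event is left out of both, and ISRs are absent from 3.15 by design. The rule differs by event type, not by table.

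**Conclusion.** The gap is real but minor. By the literal text, a non-ISR event with blank causality is left out of six drug-related tables, and this omission acts in one direction only. The size is 0.87 points per affected participant, or 0 to 4.3 points for an assumed 0 to 5 of 115. One blank is enough to drop a term from Table 3.17.

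A reader might conclude that the drug-related tables *are* understated. The SAP does not support that: it would require blanks to remain at freeze and some of those events to be truly related, and neither is shown. Nor does the SAP say that a blank means not related; the exclusion follows from a YES-only definition. The supported statement is that counts *can* be too low.

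Section 2.4 plans no hypothesis testing, there is one treatment group, and all events are also reported regardless of causality. No comparison or decision rule turns on these counts.

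**What to change.** In Section 13.6.4, replace the two lines with one rule: *Drug-related if the relationship is marked YES or is missing, for all adverse events.* Footnote each drug-related table with the number of events counted as related only because the field was missing. Add EOS to the deliverables for Listing 28, so that the records behind the footnote can be seen at both analyses.

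The cost is one sentence of SAP text, one derivation line, a footnote and one extra run of a listing. The downside is that drug-related counts may be slightly higher and may include some unrelated events, which the footnote makes visible. If the sponsor prefers not to impute causality, a separate missing category or a footnoted count of blanks would also close the gap. If no fields are blank at freeze, no table count changes.

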13.10.2. Hyperglycaemia

Medical concept of Hyperglycaemia/new onset diabetes mellitus - SMQs (1)
 'Hyperglycaemia/new onset diabetes mellitus (SMQ) Narrow SMQ code 20000041.

SMQ: 'Hyperglycaemia/new onset diabetes mellitus'; SMQ Code: 20000041	
Sub-SMQ: 'Hepatic failure, fibrosis and cirrhosis and other liver damage-related	
Category: A	
Scope: Narrow	
Preferred Term	PT Code
Acquired lipoatrophic diabetes	10073667
Blood 1,5-anhydroglucitol decreased	10065367
Blood glucose increased	10005557
Diabetes complicating pregnancy	10012596
Diabetes mellitus	10012601
Diabetes mellitus inadequate control	10012607
Diabetes with hyperosmolarity	10012631
Diabetic arteritis	10077357
Diabetic coma	10012650
Diabetic coronary microangiopathy	10080788
Diabetic hepatopathy	10071265
Diabetic hyperglycaemic coma	10012668
Diabetic hyperosmolar coma	10012669
Diabetic ketoacidosis	10012671
Diabetic ketoacidotic hyperglycaemic coma	10012672
Diabetic ketosis	10012673
Diabetic metabolic decompensation	10074309
Diabetic wound	10081558
Euglycaemic diabetic ketoacidosis	10080061
Fructosamine increased	10017395
Fulminant type 1 diabetes mellitus	10072628
Gestational diabetes	10018209

SMQ: 'Hyperglycaemia/new onset diabetes mellitus'; SMQ Code: 20000041	
Sub-SMQ: 'Hepatic failure, fibrosis and cirrhosis and other liver damage-related	
Category: A	
Scope: Narrow	
Preferred Term	PT Code
Glucose tolerance impaired	10018429
Glucose tolerance impaired in pregnancy	10018430
Glucose urine present	10018478
Glycated albumin increased	10082836
Glycosuria	10018473
Glycosuria during pregnancy	10018475
Glycosylated haemoglobin abnormal	10018481
Glycosylated haemoglobin increased	10018484
Hyperglycaemia	10020635
Hyperglycaemic hyperosmolar nonketotic syndrome	10063554
Hyperglycaemic seizure	10071394
Hyperglycaemic unconsciousness	10071286
Impaired fasting glucose	10056997
Insulin resistance	10022489
Insulin resistant diabetes	10022491
Insulin-requiring type 2 diabetes mellitus	10053247
Ketoacidosis	10023379
Ketonuria	10023388
Ketosis	10023391
Ketosis-prone diabetes mellitus	10023392
Latent autoimmune diabetes in adults	10066389
Monogenic diabetes	10075980
Neonatal diabetes mellitus	10028933
New onset diabetes after transplantation	10082630
Pancreatogenous diabetes	10033660

SMQ: 'Hyperglycaemia/new onset diabetes mellitus'; SMQ Code: 20000041	
Sub-SMQ: 'Hepatic failure, fibrosis and cirrhosis and other liver damage-related	
Category: A	
Scope: Narrow	
Preferred Term	PT Code

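### The DAIDS laboratory direction table in SAP 13.6.4 gives graded glucose, sodium and potassium values above the midpoint the same hypo- label as those below it

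*SAP*

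**What the plan says.** Under the DAIDS grading of laboratory toxicities, SAP section 13.6.4 first explains why a direction rule is needed: "Toxicity grades provided by the central laboratory do not distinguish between abnormally high or low criteria, when both are relevant for a particular parameter". It then gives the rule: "When summarizing toxicity grades for such parameters, they will be categorized as to whether they are above or below the midpoint of normal range". A three-row table follows, with one column for Grade 1 or higher values below the midpoint and another, headed "Above Midpoint for those" Grade 1 or higher, for those above it. Its rows read:

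- "Glucose Hypoglycaemia Hypoglycaemia"
- "Sodium Hyponatremia Hyponatremia"
- "Potassium Hypokalaemia Hypokalaemia"

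The first version of the RAP, which is in the same file, has the same three rows in its own section 13.6.4.

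**The concern.** The sentence separates high from low, but the table gives both sides one name. A programmer who takes category labels from the table would call a graded high potassium hypokalaemia, and would do the same for high sodium and high glucose. No other part of the SAP assigns a direction to a laboratory grade, so nothing elsewhere corrects the labels.

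The displays exposed are the chemistry summaries of maximum grade increase after baseline: Table 3.28, which is delivered at the Month 12 headline, Month 12 and end of study, and Table 3.29, its oral lead-in counterpart. High and low abnormalities of these analytes mean different things clinically, so a safety reader needs the direction to be right.

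**Working it through.** The plan gives no figure to reproduce here, and no power or error-rate calculation is involved. The check sets the rule beside the table.

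**1. Rule against table (SAP 13.6.4)**

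| Parameter | Below midpoint, as printed | Above midpoint, as printed | Above midpoint, as the rule implies |
|---|---|---|---|
| Glucose | Hypoglycaemia | Hypoglycaemia | Hyperglycaemia |
| Sodium | Hyponatremia | Hyponatremia | Hypernatremia |
| Potassium | Hypokalaemia | Hypokalaemia | Hyperkalaemia |

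Cells: 3 parameters × 2 columns = 6. As printed, 6 are hypo- and 0 are hyper-. The rule implies 3 and 3. The three below-midpoint cells are right and the three above-midpoint cells are wrong.

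**2. Could this be a misreading of the PDF?** All three rows agree in both RAP versions. The extracted text also keeps the two prefixes apart elsewhere: the seizure list in 13.10.14 has separate hyperglycaemic and hypoglycaemic seizure terms. On the other side, the extraction does swap similar words. One preferred-term code in 13.10.14 (10081179) reads as myoclonic-ataxic seizures in one RAP version and myoclonic-tonic in the other. A misreading of three cells in two versions is unlikely but not excluded.

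**3. Which outputs use the table?**

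- Tables 3.28 and 3.29 summarise chemistry by grade, so they depend on it.
- Tables 3.26 and 3.27 summarise chemistry values and changes numerically, so they do not.
- The hyperglycaemia AESI (13.10.2, Table 3.56) is selected by MedDRA terms under the heading "Medical concept of Hyperglycaemia/new onset diabetes mellitus", so it does not. The same holds for adverse event tables generally.

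**4. How many results?** This cannot be computed, because the SAP holds no laboratory data. The Schedule of Activities (13.2.1.1) has a separate glucose row marked at screening only, while Tables 3.28 and 3.29 concern increases after baseline. Whether glucose is also in the chemistry panel is not shown, so the number of affected glucose results could be zero. Sodium and potassium have no row of their own; the assumption is that they are measured in the panel.

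**The case against.** The strongest reply is that the introducing sentence is itself the rule, and that it is complete and correct. The table only names the two categories, and it keeps separate columns for them. On that view this is a typing slip that any competent programmer would put right, in descriptive tables of a study that tests no hypothesis. Most of this stands. The intended meaning is not in doubt, and the slip does not alter the method. What does not stand is leaving it alone: the table is an operative specification, and a safety display should not depend on a programmer overriding it.

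A reader might also infer three stronger consequences, none of which the document supports.

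- *Every case of hyperglycaemia, hypernatraemia or hyperkalaemia would be reported as its opposite.* Only graded laboratory results in Tables 3.28 and 3.29 are exposed. Reported events follow MedDRA coding.
- *High and low values would be pooled in one row, or hyper- rows would stand empty.* Row layout comes from the LB16 display standard, which is not shown. Read literally, the plan gives two categories with the same name. Pooling is possible, and could hide a change from a low grade at baseline to an equal high grade later, but the text does not say that it would happen.
- *The laboratory tables would contradict the hyperglycaemia AESI table.* The two count different things, coded events and laboratory grades, so a difference between them would not be a contradiction.

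**Conclusion.** Wrong as written; minor. For all three parameters listed, the above-midpoint label contradicts the sentence that introduces the table, and the RAP amendment carried the error forward from the first version. If followed literally, the effect is a wrong direction label on graded high values of glucose, sodium and potassium in Tables 3.28 and 3.29, and nowhere else. Its size in participants or results is unknown, and for glucose may be nil. The conclusion rests on two assumptions: that the printed PDF shows the cells as extracted, and that programmers would take the labels from this table rather than from the sentence above it.

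**What to change.** Check the three cells in the source PDF. If confirmed, change the above-midpoint entries to Hyperglycaemia, Hypernatremia and Hyperkalaemia. Then check that the programs for Tables 3.28 and 3.29 derive maximum grade increase separately by direction for these analytes, as the text already intends. If the Month 12 versions have been produced, check their row labels too. The cost is three table cells and a short programming check; no data collection or analysis method changes.
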